## 5.5. Packaging and Labeling

DCC-2618 will be supplied by the Sponsor as formulated drug in tablets for oral administration containing 50 mg of study drug in 30-count high-density polyethylene (HDPE) bottles with child resistant caps.

Sutent® (sunitinib malate) 12.5 mg oral capsules will be supplied in its original form in 30 count HDPE bottles and relabeled by the Sponsor.

Study drug labeling will be in accordance with applicable local and national regulations. Study drug will be provided and replaced via the Interactive Response Technology (IRT). Study drug dispensation instructions will be provided in the Pharmacy Manual.

## 5.6. Study Drug Storage Conditions

DCC-2618 bottles must be stored tightly closed between 5°C-25°C (41°F-77°F). Keep away from areas of high humidity and sunlight (i.e. near showers in bathrooms) and according to the instructions provided in the Pharmacy Manual. Excursions between 2°C-27°C (35.6°F-80.6°F) are allowed.

Instructions regarding the storage and handling of DCC-2618 after dispensation to patients will be provided to site in the Pharmacy Manual.

Refer to the provided package insert for information on sunitinib storage and handling.

While at the clinical site, study drug must be stored in a secure, temperature-monitored area of limited access and only at the location(s) listed on the Form FDA 1572 or Investigator statement.

## 5.7. Study Drug Compliance

To ensure study drug compliance, the Investigator or designee must supervise all study drug dosing that occurs at the site. At each visit, site personnel must review that the patient is compliant with study drug dosing and remind the patient of study drug dosing requirements. Compliance must also be assessed by ongoing study drug count.

If a patient demonstrates continued noncompliance of study drug dosing despite educational efforts, the Investigator must contact the Sponsor to discuss discontinuation of the patient from the study.

## 5.8. Study Drug Accountability

Accountability for the study drug at the study site is the responsibility of the Investigator. The Investigator must ensure that the study drug is used only in accordance with this protocol. Where allowed, the Investigator may choose to assign drug accountability responsibilities to a pharmacist or other appropriate individual. Drug accountability records indicating the study drug's delivery date to the site, study drug inventory at the site, study drug dispensed to each patient, study drug returned by each patient, and study drug returned to the Sponsor or study drug destruction on site must be maintained by the clinical site. Accountability records must include dates, quantities, bottle numbers, and patient numbers. The study monitor must review drug accountability at the site on an ongoing basis during monitoring visits. If any dispensing errors or discrepancies are discovered, the Sponsor must be notified immediately.

Patients must be instructed to return all unused, partially used, and used study drug bottles to the site at each visit. The study monitor must verify study drug records and inventory throughout the study.

### **5.9. Disposal, Return, or Retention of Unused Study Drug**

Patients must be instructed to return all used, partially used, and full study drug bottles. The site staff or pharmacy personnel (as appropriate) must retain all materials returned by the patients until returned to Sponsor or destroyed by the study site. If the study drug will be destroyed at the study site, the Investigator or designee, must ensure that the materials are destroyed in compliance with applicable environmental regulations, institutional policy, and any special instructions provided by the Sponsor. Destruction must be adequately documented.

### **5.10. Method of Assigning Patients to Treatment**

Patients will be randomized in a 1:1 ratio to DCC-2618 150 mg or sunitinib 50 mg. Up to 10% of randomized patients may have KIT/PDGFR WT GIST (wild-type KIT and wild-type PDGFR regardless of the mutational status of any other gene). Randomization will be stratified by:

- Mutational Status: KIT exon 9 mutation; KIT exon 11 mutation; KIT/PDGFR WT; or other KIT (absence of exon 9 or 11)/PDGFR mutations
- Intolerance to imatinib (Yes or No)

The IRT will be used to assign study drug treatment. Detailed instructions for randomization will be provided separately.

### **5.11. Blinding and Unblinding**

This is an open-label study.

### **5.12. Prior and Concomitant Treatment and Procedures**

#### **5.12.1. Prior Medications and Procedures**

Information regarding any medication including vitamin supplements, over-the-counter medications, and oral herbal preparations or non-drug therapy taken, or procedure performed within 30 days prior to signing informed consent and before the first dose of study drug must be documented in the patient's source documents and the electronic case report form (eCRF).

#### **5.12.2. Prior Anticancer Medications and Procedures**

Any prior anticancer medication or procedure must be documented in the patient's source documents and the eCRF.

#### **5.12.3. Concomitant Medications**

All medications, including vitamin supplements, over-the-counter medications, and oral herbal preparations; non-drug therapies taken on or after the first dose of study drug through and including 30 days after the last dose of study drug must be documented in the patient's source documents and the eCRF. In addition, any new treatments taken after the last dose of study drug through 30 days after the last dose must be documented in the patient's source documents and the eCRF.

### 5.12.3.1. Permitted Medication

Patients may receive medications for symptomatic relief (e.g. analgesics, laxatives, antiemetics) as long as they are not prohibited by the protocol.

For sunitinib, refer to the approved package insert or institutional guidelines.

### 5.12.3.2. Prohibited Medications and Substances

Prohibited medications and certain foods are not allowed from screening through the Safety Follow-up Visit. Except for study drug, anticancer therapies active or potentially active against GIST are prohibited during this study.

Prior to randomization, all patients must follow the exclusions listed below:

- Treatment with imatinib within 10 days prior to the first dose of study drug, or any other anticancer medication or line of therapy for advanced GIST.
- Strong or moderate inhibitors or inducers of CYP3A4, including certain herbal medications (e.g. St. John's Wort): discontinue at least 14 days (or 5x the half-life, whichever is longer) prior to the first dose of study drug.
- Please refer to the Indiana University Department of Medicine website: (<http://medicine.iupui.edu/clinpharm/ddis/main-table/>) for guidance on medications that inhibit CYP3A4 enzymes.
- Grapefruit or grapefruit juice: must not be consumed at least 14 days prior to first dose of study drug
- Known substrates or inhibitors of BCRP transporters: discontinue at least 14 days or 5x the half-life (whichever is longer) prior to the first dose of study drug.
- Please refer to the FDA's website: (<http://www.fda.gov/Drugs/DevelopmentApprovalProcess/DevelopmentResources/DrugInteractionsLabeling/ucm093664.htm>) for inhibitors and substrates for BCRP.

After randomization and during the study, patients randomized to sunitinib will follow the approved package insert or institutional guidelines for prohibited medications.

The following are prohibited after randomization and during the study for patients randomized to DCC-2618:

- Strong and moderate inducers of CYP3A, including certain herbal medications (e.g. St. John's Wort)

Please refer to the Indiana University Department of Medicine website (<http://medicine.iupui.edu/clinpharm/ddis/main-table/>) for guidance on medications that induce CYP3A4 enzymes.

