21. All Patients (optional): Additional tumor tissue samples may be collected at the EOT visit and/or for patients undergoing medical procedures including resection of metastases while on study or for patients that have disease progression if the patient consents and these samples will be used for further molecular testing of the cancer while treated with study drug.
  22. Radiologic imaging must be performed within 21 days prior to the first dose of study drug. Radiologic imaging performed as standard of care prior to informed consent may be used as the Screening assessment as long as the imaging was performed within 21 days prior to the first dose of study drug. CT scans of the pelvis, abdomen, and chest will be performed at screening. Subsequently, CT scans of the pelvis and abdomen will be performed at Days 1 of Cycles 2-7, and Day 1 of every odd-numbered cycle thereafter (e.g. Cycles 9, 11, 13 etc.) and EOT visit. A scan at the EOT visit is not required if disease progression was previously confirmed by independent radiologic review or if less than 28 days have passed since the last scan was performed. CT scans of the chest will only be performed subsequently, if the patient had lung metastases at screening or in case of lung symptoms (per the Investigator's discretion). Radiologic imaging may be performed up to 7 days prior to the corresponding study visit or post dose at the study visit. Following Cycle 7 Day 1, any initial indication of a partial or complete response based on investigator assessment must be confirmed  $\geq 4$  weeks following initial response. MRI scans of the abdomen/pelvis and CT scan without contrast of the chest can be used for patients who are allergic to radiographic contrast media or at the Investigator's discretion based on the best interest of the patient after discussion with the Sponsor. Additionally, for patients whose local regulatory authority and/or ethics committee has not approved use of CT scans, MRIs may be used. For each patient, the same assessment technique must be used throughout their participation on study unless there is a safety risk as determined by the Investigator. Ultrasound scanning is not an acceptable substitute for CT scanning.  

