#### 3.3. Duration of Study

Patients will be treated until they develop progressive disease as per mRECIST, experience unacceptable toxicity, or withdraw consent. At the time of progressive disease by mRECIST, based on independent radiologic review, patients will discontinue study drug. Patients will be eligible to receive study drug for up to 2 years. This will be extended by agreement between the Sponsor and Investigator for patients who exhibit evidence of clinical benefit and tolerability to the drug, and who adhere to the study procedures. The study will end following the last patient last visit.

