#### **5.12.4. Concomitant Procedures**

All procedures performed on or after the first dose of study drug through and including 30 days after the last dose of study drug must be documented in the patient's source documents and the eCRF.

Surgical resection or palliative radiotherapy during study treatment must be discussed with the Sponsor prior to implementation. Patients with PR are permitted resection of remaining tumor, but only after they have been on treatment for 12 months. If the Investigator believes it is in the best interest of the patient, surgical resection or palliative radiotherapy may be performed after discussion with the Sponsor. The patient will be censored in the PFS analysis from the time surgery or radiotherapy was performed.

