### 6.4. Follow Up

Patients will be contacted by phone call for the Safety Follow-up Visit 30 days (+5 days) after the last dose of study drug to assess AEs; medications, including anticancer treatments; and procedures (see Section [6.11.11](#) for further details). Patients will be contacted by phone call for OS and PFS2 (see Section [6.10.2](#) for further details).

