#### **6.11.11. Safety Follow Up**

All patients must be followed for AEs; medications, including any anticancer treatments; and procedures until 30 days (+5 days) following the last dose of study drug.

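### Protocol 5.12.3.2 bars other GIST-active therapy until 30 to 35 days after last dose, with no visible release after IRR-confirmed progression, in conflict with Protocol 7.10 and SAP 9.2

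*Protocol*

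**What the plan says.** Protocol 5.12.3.2 opens with a time limit for everything it prohibits: "Prohibited medications and certain foods are not allowed from screening through the Safety Follow-up Visit". The next sentence names the class that matters here: "Except for study drug, anticancer therapies active or potentially active against GIST are prohibited during this study". Rules before randomization and rules by arm follow. None of them says what happens once study drug has been stopped for good.

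Protocol 3.3 requires the stop: "At the time of progressive disease by mRECIST, based on independent radiologic review, patients will discontinue study drug". Table 1 puts the EOT visit within 7 days after the last dose and the Safety Follow-up, a phone call, at 30 days (+5). Footnote 22 of Table 1 waives the last scan for these patients: "A scan at the EOT visit is not required if disease progression was previously confirmed by independent radiologic review".

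Other sections deal with new therapy after the last dose:

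- Protocol 7.10 closes the safety reporting period, otherwise 30 days after last dose, when a new anticancer therapy begins.
- SAP 9.2 closes the treatment-emergent window at day 30 or the day before new anticancer drug therapy, whichever is earlier.
- Protocol 6.10.2 collects the next line of therapy, its start date and progression on it. Protocol 9.8.5.3.3 analyses PFS2 from the start of that therapy.
- Protocol 6.4 has the day-30 call "to assess AEs; medications, including anticancer treatments; and procedures". Protocol 6.11.11 says "All patients must be followed for AEs; medications, including any anticancer treatments; and procedures until 30 days (+5 days) following the last dose". Protocol 5.12.3 says "any new treatments taken after the last dose of study drug through 30 days after the last dose must be documented".

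Protocol 5.12.4 gives a permission route for local treatment: "surgical resection or palliative radiotherapy may be performed after discussion with the Sponsor". There is no matching route for systemic therapy.

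**The concern.** A patient with IRR-confirmed progression must stop study drug. On the wording of 5.12.3.2, that patient may then take no other GIST-active drug until the Safety Follow-up call. A site that complies leaves a progressing patient without active treatment for about a month. A site that treats sooner does what 7.10 and SAP 9.2 foresee, but departs from 5.12.3.2 and must document a deviation under Protocol 11.2. Two sites can therefore handle the same patient differently and each cite the protocol.

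The stake is patient care and consistent conduct. It is not the validity of the primary test.

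**Working it through.** The plan gives no figure to reproduce. The check is a comparison of sections plus simple date arithmetic.

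**1. Length of the wait.** The Safety Follow-up is at 30 days (+5) after last dose (Protocol 6.4, Table 1), so the prohibition ends between day 30 and day 30 + 5 = 35. The EOT visit is due by day 7 (Table 1, Protocol 6.3). Ending the prohibition at EOT would shorten the wait by at least 30 − 7 = 23 days for a day-30 call and 35 − 7 = 28 days for a day-35 call.

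**2. Whether any text releases the patient.** Nothing visible in 5.12.3.2 does. The 5.12.4 route covers surgery and radiotherapy only. In 6.10.1 the paragraph on IRR confirmation of progression is mostly blacked out. Instructions for this patient could sit there, so an exception cannot be excluded. 5.12.3.2 does not refer to one.

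**3. Which sections conflict, and how strongly.**

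| Place | What it does | Weight |
|---|---|---|
| Protocol 7.10 | Ends safety reporting at the start of new anticancer therapy | Strong: the period ends at day 30 anyway, so the cut works mainly for starts before day 30 |
| SAP 9.2 | Ends the treatment-emergent window the day before new therapy, if before day 30 | Strong, same reason |
| Protocol 6.10.2, 9.8.5.3.3 | Collect next-line therapy and time PFS2 from it | Shows that next-line therapy is expected on study, but not when it may start |
| Protocol 5.12.3, 6.4, 6.11.11 | Record treatments to day 30 (+5) | Weak: recording a drug is not permission to take it |

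**4. What the wait protects for an IRR-confirmed progressor.** The EOT scan is waived (Table 1, footnote 22), and after EOT only phone contacts are scheduled. Under SAP 8.1.1, new therapy censors PFS only if it precedes the event; progression on the day new therapy starts still counts. The progression is already recorded, so later therapy cannot remove it.

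**5. What the wait protects for a patient without IRR-confirmed progression.** Here SAP 8.1.1 does apply. New therapy before an event censors PFS at the last evaluable progression-free scan before that therapy, so a later progression or death is lost to the primary analysis. The sample size allows for 20% dropout without IRR progression or death. Read as a share of patients, that is 0.20 × 426 ≈ 85. The two groups need different rules.

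**6. How many are affected.** The documents do not say. For scale, about 262 PFS events are planned among 426 patients, not split between progression and death, and nothing says how soon next-line therapy would otherwise start.

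**The case against.** The strongest reply is that the intent is plain. The rule sits under concomitant medications, and a prohibition during study treatment is probably what was meant. Inclusion criterion 11 limits the bar on other interventional trials to the treatment period. This is therefore a drafting defect. That stands, but it does not settle the matter: the sentence running to the Safety Follow-up Visit takes the rule past the end of dosing, and sites are monitored against the text.

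A second reply is that a month free of new therapy keeps adverse events attributable to study drug. That is a legitimate reason for such a rule. The plan, however, already handles attribution another way, by cutting the window at new therapy (7.10, SAP 9.2). It could also be said that those cuts exist only to handle off-protocol starts. That is possible, but neither section presents them so.

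Third, the redaction in 6.10.1 is a real limit on certainty.

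A reader might infer stronger points, which the documents do not support:

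- *That next-line therapy is barred for the whole study.* The closing words of "Except for study drug, anticancer therapies active or potentially active against GIST are prohibited during this study" could be read that way, since the study ends at the last patient's last visit. The planned PFS2 collection makes that reading untenable.
- *That 5.12.3, 6.4 and 6.11.11 authorise early therapy.* They only require it to be recorded.
- *That the harm can be expressed as a percentage progressing during the wait.* The only untreated benchmark, the placebo median PFS of 6.0 weeks in Protocol 1.4, comes from patients entering second-line treatment, measured in that trial. It does not describe patients who have already progressed one line later.

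**Conclusion.** The point holds as a conflict in the wording. For patients permanently off study drug after IRR-confirmed progression, 5.12.3.2 imposes a wait of 30 to 35 days from last dose that 7.10 and SAP 9.2 do not assume and that protects no scheduled efficacy measurement in this group. The consequence is either delayed next-line therapy or a recorded deviation.

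Alpha, power and the PFS events already recorded for these patients do not change. The number affected is unknown. The conclusion assumes that the blacked-out text in 6.10.1 contains no exception and that sites apply 5.12.3.2 as written. It should be corrected because the change is small and the patients concerned have progressing disease.

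**What to change.** Add one sentence to Protocol 5.12.3.2: *For patients permanently discontinued from study drug after IRR-confirmed progression, the prohibition on other GIST-active anticancer therapy ends once the EOT assessments are done; any washout follows the label of the next therapy.* If the redacted part of 6.10.1 already says this, a cross-reference from 5.12.3.2 is enough.

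Leave the rule as it is for patients who stop without IRR-confirmed progression, unless the Sponsor agrees otherwise. A general release at EOT would make it easier for them to start new therapy early and be censored in the primary analysis.

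The cost is one sentence, with no new visit, scan or analysis. The downside is that adverse event reporting ends earlier for those who start new therapy before day 30, as 7.10 and SAP 9.2 already provide. A label washout may take back part of the 23 to 28 days gained.

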### 5.12.3.3. Medications to Avoid if possible or Take with Caution

After randomization and during the study for patients randomized to DCC-2618, the following medications should be avoided if possible or taken with caution following discussion with the Sponsor for patients receiving DCC-2618 (sites will be provided with updated information during the study):

- Strong or moderate inhibitors of CYP3A including grapefruit juice

- Known substrates or inhibitors of BCRP transporters and P-glycoprotein 1 (permeability glycoprotein, also known as MDR1). Please refer to the FDA's website for inhibitors <http://www.fda.gov/Drugs/DevelopmentApprovalProcess/DevelopmentResources/DrugInteractionsLabeling/ucm093664.htm>
- Medications dependent on CYP2C8 for their metabolism. Please refer to the Indiana University Department of Medicine website (<http://medicine.iupui.edu/clinpharm/ddis/main-table/>) for guidance on these medicines.

Patients taking any of the above listed medications must be closely monitored for any potential drug-drug interactions with DCC-2618.

For sunitinib drug-drug interactions, refer to the approved package insert or institutional guidelines.

#### **5.12.4. Concomitant Procedures**

All procedures performed on or after the first dose of study drug through and including 30 days after the last dose of study drug must be documented in the patient's source documents and the eCRF.

Surgical resection or palliative radiotherapy during study treatment must be discussed with the Sponsor prior to implementation. Patients with PR are permitted resection of remaining tumor, but only after they have been on treatment for 12 months. If the Investigator believes it is in the best interest of the patient, surgical resection or palliative radiotherapy may be performed after discussion with the Sponsor. The patient will be censored in the PFS analysis from the time surgery or radiotherapy was performed.

#### **5.13. Other Precautions**

In order to mitigate the potential risk of photoirritation/phototoxicity, patients who are taking DCC-2618 must be instructed to avoid strong sunlight, sunlamps, and other sources of ultraviolet radiation for the duration of the study. Prophylactic skin care recommendations for all patients taking DCC-2618 include sunscreen with SPF  $\geq 30$ , hypoallergenic moisturizing creams or ointments for dry skin, and gentle skincare with fragrance-free soaps and detergents.

For sunitinib precautions, refer to the approved package insert or institutional guidelines.

## 6. STUDY ASSESSMENTS

### 6.1. Screening

Screening must occur within 28 days prior to the first dose of study drug to confirm that patients meet the selection criteria for the study. Radiologic imaging and dermatologic examination must be performed within 21 days prior to the first dose of study drug. The assessments to be conducted at screening are provided in [Table 1](#) (schedule of assessments).

